University of Kansas Medical Center
RESEARCH PROTOCOL INVOLVING HUMAN SUBJECTS
TEMPLATE WITH GUIDANCE

Version date: 5/24/2018

Principal Investigator: [name]

Study Title: Informing Tobacco Treatment Guidelines for African American Non-Daily Smokers

Co- Investigator(s): [name], [name], [name]

(NOTE: not all sections of this template will apply to all projects. "N/A" is an acceptable response.)

I. PURPOSE, BACKGROUND AND RATIONALE

A. Aim and Hypotheses

Non-daily smokers, i.e., those who smoke on some but not all days, represent a substantial and growing proportion of racial/ethnic minority smokers. 1 out of 4 African Americans (AA) are non-daily smokers. AAs experience disproportionately greater smoking attributable morbidity and mortality at lower levels of smoking and AA non-daily smokers have strikingly higher levels of nicotine and the potent carcinogen, NNAL, than White and Hispanic non-daily smokers, despite a comparable level of smoking. To date, however, no evidence-based treatment guidelines exist for non-daily smokers, leaving health care providers wondering how to treat this high risk and growing subgroup, and **no** fully powered studies have been conducted to explore treatment options for non-daily smokers.

The specific aims of our study are to:

- 1) **Compare abstinence rates among AA non-daily smokers receiving either smoking cessation counseling (C) or smoking cessation counseling in combination with NRT (C+NRT).** Hypotheses: Participants randomized to C+NRT will have significantly higher biochemically verified smoking abstinence than participants randomized to C at 12 weeks end of treatment (primary outcome) and at 26 week follow-up.
- 2) **To compare patient- and provider-desired outcomes -- e.g., nicotine intake, carcinogen exposure, number of days abstinent, and side effects -- among AA non-daily smokers receiving C versus C+NRT and, within the C+NRT group, examine choice and use of NRT during the treatment period.** Hypothesis: Participants randomized to C+NRT will demonstrate significantly greater reductions in nicotine intake and carcinogen exposure and significantly more days abstinent, while experiencing no differences in side effects as participants randomized to C.

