To date, no studies have explored treatment options for non-daily smokers and, as a result, treatment guidelines are not available to guide patients or healthcare providers. The study will compare two treatments -- smoking cessation counseling alone versus counseling in combination with patients' choice of nicotine patch, gum, or lozenge -- on their effects on quitting smoking and reducing exposure to nicotine and cancer causing agents. Findings will identify which patients are most likely to benefit from each form of treatment (counseling, nicotine gum, patch, or lozenge) and will allow patients and providers to estimate their chances of success based on personal characteristics – for example, age, gender, level of smoking – and the treatment they chose. This study will determine if NRT is safe and effective for AA non-daily smokers. The program will be the first to examine treatment options for non-daily smokers and could directly contribute to the first evidence-based guidelines for treating the 9.7 million U.S. adult non-daily smokers for whom no guidelines currently exist.

[figure not shown]
II. RESEARCH PLAN AND DESIGN

A. Study Objectives

The objective of this study is to examine if NRT is an effective treatment option for AA non-daily smokers. Outcomes will be measured at weeks 12 and 26 and will include biologically confirmed smoking abstinence, nicotine intake, carcinogen exposure, days abstinent, NRT adherence and side effects.

B. Study Type and Design:

The proposed study is a randomized trial of 384 AA non-daily smokers randomized to receive either 5 sessions of smoking

Projected sample size by group using 2:1 randomization, whereby 67% are randomized to C+NRT and 33% are randomized to C

cessation counseling in combination with 12 weeks of nicotine patch, gum, or lozenge (C+NRT) or 5 sessions of smoking cessation counseling alone (C). We will use 2:1 randomization; for every patient randomized to C, two will be randomized to C+NRT (see Figure). The primary outcome is biologically-confirmed 7-day abstinence from smoking at 12 weeks. Patient- and provider-driven secondary outcomes include reductions in nicotine intake and carcinogen exposure, days abstinent, NRT adherence and side effects. Participants will be recruited from the University of Kansas Medical Center (KUMC) and Swope Health Central, a community-based primary care clinic in urban Kansas City that serves a predominately AA clientele.

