Participants will be AA adults over the age of 18 who smoked on 4-27 days out of the past 30 at enrollment and have smoked at this non-daily rate for ≥ 3 months. The study will be open to both men and women. We have chosen to focus on AAs only because their unique smoking profile places them at greater risk for tobacco-related disease and death^{44,45,50-52} Importantly, this study represents a starting point for future work that can be expanded to other ethnic groups with high rates of non-daily smoking.

Inclusion Criteria

Inclusion criteria are displayed in the adjoining table. Participants must have smoked 100 cigarettes or little cigars in their lifetime to ensure that

they are smokers and to have smoked at their current rate for ≥ 3 months to avoid enrolling smokers who are in the transitory stages of smoking initiation or reduction/cessation.

Participants also cannot be daily users of other tobacco products, not including e-cigarettes. Other racial groups will be excluded as our primary aim is to evaluate NRT in AA smokers.

Eligibility Criteria

Inclusion Criteria	Exclusion Criteria

 • African American ≥ 18 years of age • Smoke 100 lifetime cigarettes • Smoke cigarettes or little cigars on 4-27 days of the past 30 days • Smoke cigarettes or little cigars at current rate for ≥ 3 months • Use of any tobacco product, not including e-cigs, on 4-27 days in last 30 • Functioning telephone • Interested in quitting smoking • Willing to take NRT for 12 weeks and complete all study procedures 	
 • Unstable cardiac condition (e.g., unstable angina or AMI in the past 4 weeks) • Plans to move from KC during the treatment and follow-up phase • Use of pharmacotherapy, including e-cigs, in the month prior to enrollment • Pregnant or breastfeeding • Another household member enrolled in the study • Unstable housing (e.g., homeless, drug/alcohol treatment center)

Exclusion Criteria

Exclusion criteria are also displayed in the adjoining table. Exclusion criteria are consistent with contraindications for nicotine gum, patch, and lozenge.¹¹

Withdrawal/Termination Criteria

There are no expected circumstances in which the subject’s participation will be terminated by the investigator.

Clarify whether a study subject may participate in another research study while participating in this research study

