NRT (C+NRT). Participants randomized to C+NRT will be given their choice of nicotine gum, patch, or lozenge to try for 3 days each. After the 3 to 9-day trial period, they will select and receive a 12 week supply of the medication of their choice. Similar NRT choice trials have been used successfully by others.⁵² This patient-centered approach was informed by our Patient Advisory Panel, who preferred these medications because of cost and over the counter availability, and our Stakeholder Advisory Panel, who felt that this patient-centered approach emulated clinical practice and would broaden the implications of our study for informing evidence-based guidelines for treating tobacco dependence in AA non-daily smokers. Nicotine gum, patch, and lozenge are all highly effective first-line medications approved for the treatment of tobacco dependence that have been shown to double the rate of quitting compared to placebo.^{11,28} NRT dosing. One of the clinical implications of this study is to inform the development of NRT dosing guidelines for non-daily smokers. We will work hand-in-hand with our providers and quitline experts to ensure that the counseling and NRT dosing protocols can be easily implemented with non-daily smokers in clinical practice and through the national quitline, Alere. We draw on our decades of experience treating AA smokers, the well-established literature on nicotine metabolism among AA smokers, and expert consensus to derive NRT dosing guidelines. Urine cotinine levels from AA daily smokers are consistent with taking in the equivalent of 8-10 mg of nicotine per day.⁴⁰ Urinary cotinine data from our NDS pilot study indicate that AA non-daily smokers have an average daily intake of cotinine that is 61% that of daily smokers or equivalent to 5.5 mg of nicotine per day.³⁵ The goal of treatment with NRT is to replace most or all of the nicotine that would have been obtained from tobacco with nicotine from the replacement product. However, not all nicotine from NRT is absorbed into the system. For a 7 mg patch, approximately 5 mg of nicotine is absorbed.⁵³ Likewise, for each 2 mg gum or lozenge, only 1 mg of nicotine is absorbed.⁵⁴ Following from the absorption rates of these products and our preliminary data indicating that AA non-daily smokers are in need of at least 5.5 mg of replacement nicotine per day, participants choosing the patch will be started on one 7 mg patch/day and those choosing gum/lozenge will be started on six 2 mg pieces/day.

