
These doses represent a starting point. To enhance the ability of our findings to be translated into practice, counselors will educate participants about the relationship between cpd and NRT dosing and empower them to tailor use to be consistent with their smoking patterns, intensity of withdrawal and craving, and level of side effects. Participants will be taught that, if the NRT dose is adequate, they may still have urges during the day, but most of the time they will not feel strong physical cravings or discomfort. They will also be educated about side effects that may indicate a nicotine overdose (nausea, vomiting, cramps, dizziness) and the need for a dose reduction (i.e., fewer pieces of gum/lozenge per day, reduction from 24 to 16 or 12 hours per day that the patch is worn), as well as symptoms of withdrawal (e.g., irritability, restlessness, anxiety) and strong physical craving that may indicate the need for a dose increase (i.e., more pieces of gum/lozenge per day, increase to longer wear or a higher dose patch). Counselors will probe for smoking level, use of NRT (days used, amount used per day), side effects, symptoms of withdrawal and craving, and general experiences with the

medication during the week 1, 4, 6, 8, and 10 sessions and will provide guidance, as necessary, to ensure that the medication is working optimally for each participant. The PI and study physician will provide oversight on questions and issues that arise related to side effects, dose reductions and/or increases.

Overview of Major Study Events

		Enroll./ Baseline					EOT	Final Follow- Up
		Wk 0*	Wk 1	Wk 4	Wk 8	Wk 10	Wk 12*	Wk 26*
Screening/ Assessments	X	X		X	X		X	X
Intervention								
Counseling		X	X	X	X	X		
Medication Dispensing (C+NRT only)		X (3 to 9- day trial period)	X	X	X		X	

*in person; all other visits are by telephone; EOT=end of treatment

Procedures and Methods

An overview of major study events is provided in the adjoining table.

Initial Screening.

The initial screen will review inclusion/exclusion criteria. Those eligible will be scheduled to complete final eligibility screening within 14 days. All ineligible smokers will be referred to local resources.

Final Screening and Enrollment (Wk 0). Final eligibility screening will be conducted in person and will consist of a pregnancy test on women of childbearing age and obtaining informed consent.

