Counseling Visits (Wks 0,1,4,8,10). Counseling sessions will be completed by phone at Wks 1,4, 8,10, and in person at Wk 0. The number of sessions is consistent with our previous studies where we have achieved visit completion rates of around 80%.^{45,55,56}

NRT Dispensing (Wks 0-1). Participants randomized to C+NRT will be given a trial supply of nicotine gum, patch, and lozenge and be instructed to try each for 3-days. After the 3 to 9-day trial period, they will select and be mailed a 4 week supply of the medication of their choice. They will receive refills of their selected medication at the Weeks 4 and 8 study visits.

Biological Sample Collection (Wk 0,12,26). Urine will be collected three times throughout the study for biochemical verification of cessation at Wk 12 and Wk 26, nicotine intake at Wks 0, 12, 26, and carcinogen exposure at Wks 0, 12, and 26. Additional details regarding each assay are provided in the Measures and Assessment Time Points table.

Retention. We have developed a system of reminders and compensation that have resulted in impressive retention rates in our previous clinical trials. Reminders. One week prior to each scheduled visit a reminder postcard noting the scheduled appointment date and time will be mailed to participants. In addition, participants will be called up to 6 times to remind them of their upcoming visit. A detailed tracking database, with an automated reminder system, will notify counselors of when to send postcards and complete reminder phone calls. Compensation. Participants will be given a \$40 electronically loaded gift card at Wks 0, 12 and a \$20 electronically loaded gift card at Wks 1, 4, 8, 10, 26 in appreciation for their time and participation.

Measures

Our selection of measures (see table) and the measurement time points have been driven by our patient and stakeholder advisory panels.

Measure and Assessment Time Points

Primary Scientific Outcome (Aim 1)

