Smoking abstinence at Wk 12 (primary cessation outcome) and Wk 26 (secondary cessation outcome). Biochemically confirmed at Wk 12 using urine anabasine and anatabine, with the recommended cut-off of 2 ng/ml to differentiate smokers from non-smokers. ⁵⁰ These tobacco alkaloids are considered the gold standard for confirming abstinence when cotinine measurements are not valid – i.e., detectable levels of cotinine could reflect NRT use or smoking. ⁵⁰ Biochemically confirmed at Wk 26 using urinary cotinine, the proximate metabolite of nicotine, with the recommended cut-off of 50 ng/ml used to differentiate smokers from non-smokers. ⁵¹ Time Points: Wk 12, 26
Secondary Patient- and Provider-Derived Outcomes (Aim 2)
Nicotine intake (total nicotine equivalents/creatinine). Assessed by urine; quantified by examining the sum of four of the major nicotine metabolites (cotinine + cotinine-glucuronide + trans-3'-hydroxycotinine + 3HC-glucuronide) to creatinine ratio using procedures described by [name] (consultant). ⁵¹ Total nicotine equivalents/creatinine represents the current gold standard for estimating nicotine intake/exposure from tobacco. ⁵⁷ To ensure that nicotine metabolites detected at Wk 12 are a result of tobacco exposure and not NRT use, we will schedule the urine collection for 7 days after the last dose of NRT. This 7-day time frame is more than adequate given the 15-20 hour (3-4 day) elimination half-life of cotinine and accounts for the substantial individual variability in the rate of elimination of nicotine. ⁵⁸ Time Points: Wks 0,12,26
Carcinogen exposure [NNAL, PAH]. Assessed by urine; quantified by examining NNAL (4-(methylnitrosamino)-1-(3)pyridyl-1-butanol) and polycyclic aromatic hydrocarbons (PAH) and specifically, 1-hydroxypyrene (1-HOP), using procedures described by [name] (consultant). ⁴⁰ While there are >70 established carcinogens in tobacco, NNAL and PAH are widely considered to be among the most important causative agents in the development of lung and esophageal cancer ^{38,39,59} and reflect the current gold standard for estimating carcinogen exposure from tobacco products. Time Points: Wks 0,12,26
Days Abstinent. Cumulative number of days abstinent Time Points: Wks 1,4,8,10,12
NRT adherence. 3-day recall of NRT use (C+NRT only) -- i.e., pieces of gum, lozenge, or number of patches used in the last 3 Time Points: Wks 4,8,12

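### The Wk 12 urine cannot fall 7 days after the last NRT dose while NRT runs for 12 weeks and Wk 12 is the end of treatment; the outcome directly exposed is Wk 12 nicotine intake

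*Combined protocol and SAP*

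**What the plan says.** The rule is in the nicotine-intake row of the Measure and Assessment Time Points table (II.E). For the Wk 12 sample, "we will schedule the urine collection for 7 days after the last dose of NRT". Its stated aim is that metabolites found at Wk 12 come from tobacco and not from NRT.

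Other sections fix the treatment period and the sampling date:

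- II.B describes the active arm as "cessation counseling in combination with 12 weeks of nicotine patch, gum, or lozenge (C+NRT", and the eligibility table in II.D requires participants to be "Willing to take NRT for 12 weeks and complete all study procedures".
- II.E, NRT (C+NRT): "After the 3 to 9-day trial period, they will select and receive a 12 week supply of the medication of their choice". II.E, NRT Dispensing, mails four weeks of product after the trial and adds: "They will receive refills of their selected medication at the Weeks 4 and 8 study visits".
- I.A places the primary hypothesis "at 12 weeks end of treatment (primary outcome", and the Overview of Major Study Events labels the Wk 12 column EOT, with the key "EOT=end of treatment".
- II.E, Laboratory Tests and Biological Sample Collection, plan three urines only, at Wks 0, 12 and 26. The Wk 12 sample serves abstinence verification, nicotine intake and carcinogen exposure.

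The counseling-session table also lists ending medication at Wk 10 as a topic. That may be a stop date, or only a subject for discussion at that session.

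**The concern.** Staff cannot keep a Wk 12 date, a 7-day washout and 12 weeks of NRT together, and the text available does not say which one governs. What gives way decides what is measured.

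If the date is kept and participants are still using NRT, total nicotine equivalents at Wk 12 include nicotine from the study product. NRT is supplied only in C+NRT, so the error falls mainly on that arm and makes its reduction in intake look smaller. Wk 12 is one of the two follow-up times in the linear mixed model for Specific Aim 2 (II.C).

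If the washout is kept after 12 weeks of NRT, the C+NRT urine moves past Wk 12. That urine also verifies the primary outcome. Its 7-day abstinence window would then lie wholly after NRT has ended, although the endpoint is labelled end of treatment. Arm C has no last dose from which to count.

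**Working it through.** **Convention.** Day 0 = Wk 0 = randomization; Wk 12 = day 84. The product trial is assumed to start on day 0 with no mailing delay; any delay moves the dates later.

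**The plan's own figures first.**
- Supply: one 4-week mailing plus refills at Wks 4 and 8 (each taken as 4 weeks) is 3 × 28 = 84 days, which agrees with a 12-week supply.
- Washout length: 7 days = 168 h. With the stated cotinine half-life of 15-20 h, 168/20 = 8.4 to 168/15 = 11.2 half-lives. The 3-4 days given in parentheses is read as about five half-lives (75-100 h = 3.1-4.2 days), not as the half-life itself. On that reading 7 days is long enough.

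**Dates.**

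| Case | Last dose | Urine | Conflict |
|---|---|---|---|
| (a) NRT ends at Wk 12, trial counted in the 12 weeks | day 84 | 84 + 7 = day 91 (Wk 13.0) | 7 days after Wk 12 |
| (b) Full supply used after the trial | 3 + 84 = 87 to 9 + 84 = 93 | 94 to 100 (Wk 13.4-14.3) | 10 to 16 days after Wk 12 |
| (c) Urine kept at Wk 12, rule kept | 84 − 7 = day 77 | day 84 | 77 − 9 = 68 to 77 − 3 = 74 supply days, i.e. 68/84 = 81% to 74/84 = 88% |
| (d) Wk 10 read as a stop | day 70 | day 84 | 14 days off NRT, but 61 to 67 supply days |

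No case satisfies every statement. Cases (a) and (b) break the urine date; (c) and (d) break the 12 weeks of NRT.

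**Size of contamination if the date is kept and the rule is not (illustration).** Inputs come from NRT dosing in II.E: usual intake equivalent to 5.5 mg nicotine per day; about 5 mg absorbed from the starting patch; 1 mg absorbed from each of six starting pieces of gum or lozenge.
- NRT intake relative to usual intake: 5/5.5 = 0.91 (patch); 6/5.5 = 1.09 (gum or lozenge).
- Fraction left d days after the last dose, half-life h hours: 2^(−24d/h).
- d = 1: 0.33 to 0.44; multiplied by 0.91 (low end) and 1.09 (high end), 0.30 to 0.47.
- d = 3: 0.036 to 0.082; 0.03 to 0.09 of usual intake.
- d = 7: 0.0004 to 0.003; 0.0004 to 0.0032 of usual intake.

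This assumes full adherence at the starting amount and one half-life for all summed metabolites.

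**The case against.** The best reply is that the washout sentence appears only in the nicotine-intake row. The abstinence row has no washout and uses anabasine and anatabine, chosen because cotinine could reflect NRT. That stands: a reader might infer that the conflict undermines primary verification, and the documents do not support this. Sample size and power are untouched.

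A second reply is that a last dose by day 77, or a stop at Wk 10, would let both arms be sampled at Wk 12 with the purpose of the washout met. That also stands, but it trades one contradiction for another, since II.B and II.D still say 12 weeks. A supply is an amount, and participants may tailor their use, so case (b) is the far end of the range.

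Third, the contamination figures describe a departure from the stated rule. That is true. They show what is at stake if the date prevails, not what the plan intends.

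Four further inferences go too far:
- That the arms are scheduled on different days. Both are assigned to Wk 12. A gap appears only if C is assumed to be seen on day 84 while C+NRT follows the washout.
- That a Wk 10 stop moves the urine to day 77. Collection is fixed at Wk 12.
- That the washout spoils the regression of cessation on NRT adherence. If the Wk 12 recall is zero for everyone, a simple mean over visits is only rescaled by a constant, which leaves the test and fitted probabilities unchanged.
- That a dispensing mark under Wk 12 in the events table proves continued treatment. The column alignment in the text available is not reliable enough for that.

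**Conclusion.** The concern holds as an internal contradiction in timing. On the plan's own figures the mismatch is 7 days if the trial counts toward the 12 weeks and 10 to 16 days if it does not. Equivalently, a day-84 urine that keeps the washout allows only 81-88% of the supply days. Confidence is high in the date arithmetic; the consequences are conditional on which statement gives way.

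The outcome directly exposed is Wk 12 nicotine intake in C+NRT. For the primary outcome, the date of the verifying urine and of its abstinence window is left open; no size or direction of bias is claimed. The length of the washout is not in question.

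One limit applies: the text between section II.H and the adverse-event reporting rules was not available, so a visit window stated there cannot be excluded. This should be fixed before the Wk 12 data are analyzed.

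**What to change.** 1. Reconcile I.A, II.B, II.D and, in II.E, the counseling-session table, the NRT and NRT Dispensing text, the events table, the urine-collection text and the nicotine-intake row. Which NRT duration or stopping point is right is for the sponsor and the investigator; none is proposed here.
2. Set one Wk 12 assessment day and window, counted from randomization, the same in both arms and compatible with the 7-day rule. Label the primary endpoint to match.
3. Record the date of last NRT use at Wk 12 in both arms, since participants in C may obtain NRT themselves.
4. State that nicotine-intake values taken within 7 days of NRT use will not be analyzed as tobacco intake, and report their number by arm.

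Cost: protocol wording, one questionnaire item and some Wk 12 intake values that cannot be used, probably mostly in C+NRT. If the visit is moved and not the last dose, the Wk 12 assessment shifts by 7 to 16 days in both arms.

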cross-sectional survey of 1,201 non-daily smokers -- 401 AA, 400 Hispanic/Latino, and 400 White.³¹⁻³⁴ Findings suggest that AA non-daily smokers are similar to White and Hispanic/Latino non-daily smokers on many factors. AA non-daily smokers are stable smokers, having smoked at their current rate for 11.4 (12.2) years, they are nicotine dependent, with 44% smoking their first cigarette within 30 minutes of waking on the days that they smoke, they suffer health consequences related to their smoking, with 23% rating their current health as fair or poor and 4%-13% living with one or more smoking-related chronic diseases (e.g., heart disease, cancer, asthma, emphysema). They also want to quit -- 62% had quit for one day or longer in the last year and 34% planned to quit in the next 6 months -- but only 24% had been offered assistance to quit by a health care provider and few had used pharmacotherapy (1%-19%) or behavioral approaches (2.2%-4.7%) to aid their attempt.

However, there are notable exceptions in our data.³⁵ AA non-daily smokers were significantly more likely than White (W) and Hispanic/Latino (H/L) non-daily smokers to use menthol cigarettes (84% versus 35% and 59%, respectively, $p < 0.0001$), which may increase the depth of inhalation and optimize the amount of nicotine delivered.^{36,37} AA non-daily smokers also had strikingly higher levels of urinary cotinine, the major metabolite of nicotine

Tobacco and Carcinogen Exposure among AA, Hispanic/Latino, and White Non-Daily Smokers ³⁵			
	AA	H/L	W
Cotinine	807.8 ng/mg	125.2 ng/mg	264.8 ng/mg
NNAL	187.6 pg/mg	64.6 pg/mg	40.7 pg/mg
Participants were equivalent on cpd on days smoked (5.0 cpd on days smoked) and days smoked in the last 30 (13.0 days smoked)			

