Specific Aim 2: To compare patient- and provider-desired outcomes -- e.g., nicotine intake, carcinogen exposure, number of days abstinent, and side effects – among AA non-daily smokers receiving C versus C+NRT and, within the C+NRT group, examine the choice of NRT and use during the treatment period. Hypothesis: Participants randomized to C+NRT will demonstrate significantly greater reductions in nicotine intake and carcinogen exposure and significantly more days abstinent, while experiencing no differences in side effects as participants randomized to C. Analytic strategy: We will utilize linear mixed models to longitudinally (week 12 and 26) compare nicotine and carcinogen exposure between the two groups, then subsequently examine the effects of the covariates listed in the measurement table above using a best subsets selection method for both nicotine and carcinogen exposure independently. A generalized linear mixed model approach will be used to model days abstinent, controlling for number of days in study, to assess the effect of treatment on this endpoint and best subsets selection will be used to examine the effects of covariates on this endpoint. For each of these models, based upon the sample size, we anticipate that ten to twelve covariates could be included in a final model. We will compare the prevalence of any side effect as well as each specific side effect, from baseline to week 12, between the two groups using the chi-square test. If there is a global difference we will examine, within the NRT group, if type of NRT impacts the side effect profile. Within the NRT group we will descriptively summarize the number and percent of subjects who choose each type of NRT. Subsequently we will describe and descriptively compare the percent of subjects within each of these subgroups who use the NRT of choice during the treatment period (i.e., percent of patients within the patch, gum, and lozenge groups who used the medication).

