Side effects. Participants will be asked about symptoms commonly associated with quitting smoking and/or NRT (i.e., difficulty concentrating, irritability, skin rash, mouth/throat irritation, nausea, sleep disturbance, heart burn) Time Points: Wks 4,8,12
Covariates (Aims 1, 2 & 3)
Demographics. Includes gender, age, income, education level, marital status, and use of alcohol Time Point: Wk 0
Smoking history. Includes type of cigarette (menthol, non-menthol), days smoked per month, number of cigarettes smoked per day on days smoked, length of time smoking at current non-daily rate, age of smoking initiation, time to first cigarette of the day (nicotine dependence), use of cigarettes only or cigarettes in combination with alternative forms of tobacco (ATP; e.g., cigars, cigarillos), presence of other smokers in the home, and home smoking restrictions Time Point: Wk 0
Treatment. Includes treatment assignment (C, C+NRT) and, for those randomized to C+NRT, their choice of nicotine gum, lozenge, or patch.

Clearly indicate which procedures, tests, visits, etc., are parts of usual standard therapy and which are performed solely for research purposes.

All tests, procedures, and visits are being performed solely for research purposes and are not billable to insurance companies.

Describe the fate of any body component (blood, CSF, bone marrow, etc.) used in the study, emphasizing confidentiality of labeling of the sample and the sample's destruction or storage.

Samples will be labeled only with a unique study identification number and only members of [name] and [name]'s team will have access to the samples. Samples will be disposed of one month after the final report is sent out to the Principal Investigator, unless participants agree to have their urine stored for future testing.

F. Risk/benefit assessment:

Physical risk

Risks for participating in the study are primarily those related to the use of NRT for participants randomized to the C+NRT arm. The safety of NRT has been demonstrated in hundreds of studies spanning over 30 years of research, including studies of patients who are very low level smokers and nonsmokers. To minimize any possible risk, we will exclude any patients with unstable heart disease (i.e., unstable angina or AMI in the past 4 weeks) per the medical contraindications for NRT.

Nevertheless, NRT, particularly in continuing smokers, can be associated with nausea, jitteriness,

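### Smoking frequency at entry strongly predicts cumulative days abstinent, but the Aim 2 treatment model does not commit to adjusting for it

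*Combined protocol and SAP*

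**What the plan says.** The Measure and Assessment Time Points table (II.E) gives the whole definition: "Days Abstinent. Cumulative number of days abstinent Time Points: Wks 1,4,8,10,12". It lists no Week 0 value and does not mention a quit-date anchor, a minimum run of days or subtraction of a baseline. In the same table, nicotine intake and carcinogen exposure do have a Week 0 measurement.

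The eligibility table (II.D) requires participants to "Smoke cigarettes or little cigars on 4-27 days of the past 30 days".

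Under Specific Aim 2 in the analysis plan (II.C), a generalized linear mixed model "will be used to model days abstinent, controlling for number of days in study, to assess the effect of treatment on this endpoint". The same sentence goes on to say that "best subsets selection will be used to examine the effects of covariates on this endpoint". The covariate list in II.E, headed for Aims 1, 2 and 3, includes "days smoked per month, number of cigarettes smoked per day on days smoked", taken at Week 0. Aim 2 hypothesizes that C+NRT yields more days abstinent than C.

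**The concern.** In daily smokers, a smoke-free day is a change in behaviour. In this trial it is a condition of entry. A cumulative count therefore mixes the smoke-free days a person would have had anyway with those gained during the study. The first part varies widely, because the eligibility window is wide.

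The variable that would separate the two parts is collected, yet nothing commits the treatment comparison to using it. Whether it enters depends on a selection step. Two things are at stake for this secondary endpoint: the precision of the between-arm comparison, and whether a reader can tell benefit from no change in a reported mean. The plan also leaves open which estimate, with or without entry frequency, tests the hypothesis.

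**Working it through.** **Inputs from the documents.** Entry frequency is 4 to 27 days per 30 (II.D). The group's earlier survey gives 13.0 days smoked of the last 30 (table in I.B). Arm sizes are 128 (C) and 256 (C+NRT), and expected Week 12 abstinence is 10% against 20% to 25% (II.C).

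**The plan's own figures.** No SD, effect size or power is stated for days abstinent. The stated power for the primary outcome is 95%, 87% and 71% for 10% against 25%, 22.5% and 20%. A two-sided 5% test of two proportions at 128 and 256 gives 95.7%, 87.6% and 71.7%, so those figures reproduce. They are not affected by this point.

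**Score with no change in smoking.** Over 84 days, counting from Week 0, a person who smokes b days per 30 scores 84 × (1 − b/30). The most that complete quitting can add is 84 × b/30.

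| Days smoked per 30 at entry | Score with no change | Largest possible gain |
|---|---|---|
| 4 | 72.8 | 11.2 |
| 13 | 47.6 | 36.4 |
| 27 | 8.4 | 75.6 |

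The two eligibility extremes differ by 72.8 − 8.4 = 64.4 days. A participant who goes from 27 to 10 days per 30 scores 84 × 20/30 = 56, below the 72.8 of the unchanged 4-day smoker.

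**Arm difference implied by the plan's quit rates.** Assume that quitters score 84 and others do not change. The difference is then (quit rate in C+NRT − quit rate in C) × 84 × mean b/30.
- Mean b = 13: 0.10 × 36.4 = 3.6 days and 0.15 × 36.4 = 5.5 days.
- Mean b = 15.5 (uniform on 4 to 27): 0.10 × 43.4 = 4.3 days and 0.15 × 43.4 = 6.5 days.

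**Chance difference between arms at entry.** With an assumed entry SD of 5 to 6.9 days per 30, the standard error of the arm difference in entry smoke-free days, scaled to 84 days, is (SD/30) × 84 × √(1/128 + 1/256). This is 1.5 to 2.1 days, centred on zero.

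**Share of variance explained by entry frequency.** These are simulations under assumptions. A linear model for the 84-day total stands in for the planned mixed model.
- *Non-quitters unchanged; 10% against 20% or 25% quitting; entry frequency uniform on 4 to 27, or centred on 13 with SD 5 or 7.* Entry frequency explains 29% to 45%. The SD falls from 18–24 to 15–19 days, and power rises from 35–78% to 58–90%. In the most favourable case the SD falls from 21.2 to 15.7, so 1 − (15.7/21.2)² = 0.45, and power rises from 35% to 58%.
- *Non-quitters cut down by 30% to 60% on average, with variation between people, in some cases more in C+NRT.* Entry frequency explains 14% to 29%. Power rises from 24–96% to 32–99%. The smallest gain in any case is 96% to 99%.
- *10% against 22.5% quitting; non-quitters smoke at about 0.7 of their entry rate with log-SD 0.3 to 0.9; entry days spread over 4 to 27.* Correlations of −0.24 to −0.60 give squares of 0.06 to 0.36.

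In the first two sets, treatment explains 0.4% to 4% of the variance. Across all three, the standard error shrinks by between 1 − √0.94 = 3% and 1 − √0.55 = 26%.

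**The case against.** The strongest reply is that the trial is randomized. Entry frequency balances in expectation, the unadjusted test has its nominal type 1 error, and its standard error already carries between-person variation, including chance imbalance. The C arm supplies the reference for the between-arm difference. All of this stands. A reader might infer that the comparison is biased, or that a chance imbalance would be mistaken for an effect more often than the nominal error rate allows; the documents do not support that.

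Second, the plan does not ignore entry frequency. It is a listed covariate, and Aim 2 expects ten to twelve covariates in a final model. The more prognostic it is, the more likely selection is to keep it. For this endpoint the plan does not say that selection follows the treatment test. This also stands, but likely inclusion is not pre-specification.

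Third, a reader might infer from the 64.4-day range that the endpoint mostly ranks people by how often they smoked at entry. The range compares the two eligibility extremes. In the scenarios, entry frequency explains 6% to 45% of the variance, so more than half of the spread always comes from elsewhere.

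Finally, the definition does not say whether counting starts at Week 0 or on a quit day, and the 13-day figure comes from a survey, not from enrolled participants who want to quit. The 84-day scores are therefore illustrations. A later start shortens the count but leaves the dependence on entry frequency in place.

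**Conclusion.** The point holds as one of precision and readability for a secondary endpoint. The count includes smoke-free days that every participant has at entry, and the stated treatment model is not committed to adjusting for how many. Entry frequency is a strong predictor: roughly 6% to 45% of the variance under the assumed scenarios, against at most 4% for treatment where that was calculated. Adjustment added about 3 to 23 percentage points of power in the scenarios where power was computed.

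These sizes rest on assumed entry distributions, cutting-down rates and counting from Week 0, because the documents give no SD or entry distribution; at the low end the gain is small. A raw mean near 48 days would also be what no change looks like at 13 days per 30, so the mean alone says little about benefit. Validity of the randomized comparison is not in question, and the primary outcome and its power are untouched. Leaving the covariate to selection is a missed opportunity, not an error.

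**What to change.** Under Specific Aim 2, pre-specify Week 0 days smoked per month as a fixed covariate, alongside time in study, in the days-abstinent model that tests the hypothesis. Name that model's treatment estimate as the test, and label best subsets selection for this endpoint exploratory. State when the count starts.

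A summary of smoke-free days beyond those expected at the participant's own entry rate can help readers, but it should be descriptive only. It should use each participant's actual days in study in place of 84, and state that its maximum depends on entry frequency (11.2 to 75.6 days over a full 84). Otherwise it reverses the dependence: a complete quitter from 4 days per 30 gains 11.2, while someone going from 27 to 10 and still smoking gains 56 − 8.4 = 47.6.

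The covariate is already collected, so the cost is a few lines of analysis-plan wording.
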